## 2.0 Objectives

**3.1 Primary Objective:** The primary objective is to estimate the 1-week change in the proportion of HCV-infected hepatocytes in participants with HCV mono-infection and HIV/HCV coinfection on therapy with two or three DAAs with different mechanisms of action using single cell laser microdissection (scLCM).

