## 3.0 Background

### 4.1 Disease Under Study

HIV infects approximately 30 million people worldwide and more than 1 million people in the US [1]. While antiretroviral therapy (ART) has dramatically decreased AIDS-related mortality, people living with HIV (PLWH) still have higher mortality than uninfected people. Liver-related mortality has consistently been found to be among the leading causes of death in PLWH in the US during the ART era, and HCV coinfection disproportionately contributes to liver disease in this population [2, 3]. Because of common routes of transmission, between 25-80% of PLWH in the US have been reported to be coinfecting with HCV [4]. HIV worsens HCV in several ways: i) by decreasing the likelihood of spontaneous clearance; ii) by increasing the HCV RNA level, iii) by accelerating the progression of HCV-related liver disease; and iv) by worsening the response of HCV to interferon (IFN)-based treatments [4]. Improved HCV therapies have reduced the gaps in efficacy between HCV mono-infected persons and HIV/HCV co-infected persons when given for standard durations of 12 weeks; however, whereas shortened therapy has delivered promising results for HCV mono-infected persons, they have been disappointing for HIV/HCV co-infected persons.

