In addition, inhibition of the HCV protease may restore innate intra-hepatic immune functions that are thought to be impaired by the virus. In response to viral replication intermediates, such as viral RNA and proteins, IPS-1 and TRIF adaptor protein act as signaling intermediates in retinoic acid-inducible gene (RIG-I) and/or Toll-like receptor 3 (TLR3) pathways. Activation of these pathways induces IRF3 activation and subsequent transcriptional activation of type I interferons (IFN- $\alpha/\beta$ ) and interferon-sensitive genes (ISGs). Type I interferons and ISGs play a major role in combating viral infections. Cleavage of IPS-1 and TRIF by HCV NS3/4A blocks the downstream signaling pathway, resulting in inefficient activation of IRF3 and severely reducing the host innate immune response against the viral infection. It is possible that HCV protease inhibitors (PI) can play a dual role in countering viral infection through a direct antiviral mechanism, as well as by abrogating the HCV protease-mediated downregulation of innate immunity pathways, such as the RIG-I and TLR3 pathways.

The comparison of the intra-hepatic HCV kinetic and immunologic response after 7 days for dosing with SOF/VEL and SOF/VEL/VOX will permit the in vivo assessment of the role of protease inhibition on hepatic clearance of HCV during DAA treatment.

The change in the timing of the second biopsy is based on investigator review of unpublished, preliminary data from A5335s was presented at the Annual ACTG Network Meeting in June 2017. In this study, two participants with HIV/HCV coinfection underwent paired liver biopsies at day 0 and day 7 of treatment with paritaprevir/ritonavir/ombitasvir + dasabuvir. In both participants, the proportion of HCV-infected hepatocytes had decreased to only 1% (Figure 1). The rationale for the second liver biopsy at day 4 is that this earlier time point will allow better understanding of this rapid and profound reduction in HCV burden and allow for the more precise modeling of HCV elimination from the liver.

Figure 1: Proportion of HCV-infected hepatocytes at Day 0 and Day 7, A5335S

The vertical axis represents the number of HCV-infected hepatocytes counted by sLCM and the horizontal axis represents the HCV RNA production of each hepatocyte in IU/mL (one IU = two copies of HCV RNA) with zero (0) representing an uninfected hepatocyte.

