Intrahepatic HCV infection was studied intensively using scLCM and spatial statistical analysis in liver tissue from four subjects of the ALIVE study of injection drug users (IDUs) who had chronic genotype 1 infection. By dissecting > 1000 individual hepatocytes, the viroscape was uncovered in eleven separate grids (Figure 2), demonstrating clusters of HCV+ hepatocytes; 21-45% of all hepatocytes were infected. HCV vRNA was measured in each hepatocyte and ranged from 1 – 50 IU across all subjects with the majority of cells producing < 10 IU. This technology has been extended to allow HCV sequencing from individual hepatocytes. Moreover, IFN responses were measured in the same hepatocytes; in contrast to clustered HCV infection, a representative ISG, IFITM3, was found to have a scattered expression pattern that was neither directed toward nor away from HCV clusters. Indeed, few HCV+ hepatocytes expressed the ISG. These results suggest poor targeting of ISG expression to HCV-infected hepatocytes, and may partly explain persistence of HCV infection. Since HCV RNA amounts are the principal measures of effective DAA treatment, scLCM with high-resolution qPCR and spatial statistical analyses form a highly innovative approach to the study of intrahepatic HCV infection before and during HCV DAAs and to study the effect of HIV coinfection on the host response.

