## 10.0 Sample Size

The anticipated sample size for analyses is 15 participants with 5 in each of three distinct groups. Group C will enroll 5 patients with HIV/HCV genotype 1a coinfection and will receive treatment with SOF/VEL representing inhibitors of HCV NS5B and NS5A a. Group A and B will

each enroll 5 patients with HIV genotype 1a mono-infection; Group A will be treated with SOF/VEL/VOX and Group B will receive only SOF/VEL representing inhibitors of HCV NS5B and NS5A only. As such, Groups B and C are treated with same two-drug DAA regimen and will permit the comparison of persons with HIV/HCV and HCV. In contrast, Groups A and B include patients with HCV mono-infection and differ by the use of the HCV NS3/4 inhibitor Voxilaprevir in Group A and will permit the comparison of the NS3/4 inhibition versus none.

Because this study is exploratory and is enrolling a very small sample, traditional statistical power calculations are not being used to justify the sample size. Instead, this sample size was developed based on the feasibility of both anticipated enrollment and the feasibility of the laboratory procedures, namely single cell laser microdissection.

For the primary outcome of difference in proportion of HCV-infected hepatocytes between week 1 and baseline, we present an approximate confidence interval around the difference in proportion within subject to show the level of precision in this exploratory single-arm study. The following assumptions are made to approximate the confidence interval in a conservative way:

- for within-subject variation – proportion of infected hepatocytes at any particular time-point is 50% (this assumption is conservative as results in maximum variation),
- the number of hepatocytes measured within each subject is 400 (this is conservative as it is estimated that between 400 and 1000 hepatocytes will be measured),
- normal approximation to the binomial for standard error estimation, and the variance of the difference will be approximated as twice the variance (assuming independence between week 1 and baseline, which is conservative except under negative correlation, which is not expected given the reported potency of the intervention being studied).

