## 11.0 Statistical Analyses Plan:

All outcomes will be summarized and described with appropriate summary statistics. For example, estimated binomial proportions (e.g., for % of HCV-infected hepatocytes) will include 95% confidence intervals. Means, medians for continuous outcomes will include confidence

intervals and key percentiles (eg, 25th, 75th percentiles), respectively. Outcomes defined as changes will also present summary distribution of values at each time point contributing to change outcome. In addition, because of small sample size, outcomes will also be summarized on a per-subject basis for reporting. Changes will be defined as absolute differences for those outcomes where baseline distribution of proportion is close to 0 or 1, and relative (and absolute secondarily), changes otherwise. For continuous outcomes, both absolute and relative changes from baseline will be explored and summarized. Confidence intervals (using exact methods) on change outcomes will be calculated and presented.

For the primary outcome, the estimated differences will be summarized and described on a per-subject basis (i.e. 15 differences and intra-subject confidence intervals). Additionally, the proportion of infected hepatocytes will be summarized across subjects at each time point and presented. Finally, the average difference from week 0 to week 1 (absolute difference) for the study sample will be estimated and summarized.

For the plasma VK secondary outcome, longitudinal modeling will be used to combine plasma HCV viral loads (VL) over the first week. For instance, marginal modeling will focus on estimation of levels across the study sample (ie, population level inference). This can be used to describe the average change in HCV VL over the first week on treatment. In addition, (generalized linear) mixed effects models will focus on subject-specific inference (ie, prediction). Since this is a small study, these data will be graphically represented by subject.

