Associations between two continuous outcomes will be described using rank-based (e.g., Spearman, using exact method versions with PROC STATXACT [specifically PROC ASSOCIAT]) correlations (and will be presented graphically using scatterplots), and associations between a continuous and a categorical outcome will be summarized by separately summarizing distribution of the continuous outcome by the other covariate category (level), as well as testing for differences in the distribution of the continuous covariate by varying levels of the categorical covariate using the exact version of Kruskal-Wallis test (equivalent to the exact version of Wilcoxon rank sum tests for more than two categories). For restricted alternatives of monotonicity among more than two groups, additional statistical tests such as Jonckheere-Terpstra may also be used.

Contingency tables will describe ordinal fibrosis staging (non-continuous outcomes), and distributions of continuous outcomes will be summarized by fibrosis stage, as necessary.

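### Section 11 gives the primary change as an unadjusted absolute difference, against its own rule preferring relative change, and names no baseline-accounting method for the A-B and B-C comparisons

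*Combined protocol and SAP*

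**What the plan says.** - Section 2.0 frames the primary objective as estimation: "The primary objective is to estimate the 1-week change in the proportion of HCV-infected hepatocytes".
- Comparisons are nonetheless intended. Hypotheses 2.1 and 2.2 (Section 1.0) predict a greater decline in intrahepatic HCV RNA in A than in B, and in HCV alone than in HIV/HCV. Section 10.0 says of Groups B and C that their shared regimen "will permit the comparison of persons with HIV/HCV and HCV", and gives A and B the same role for the protease inhibitor. It also averages the differences within each group of five.
- Section 11.0 reports the primary outcome as 15 individual differences with intervals, as proportions across subjects at each time point, and then: "Finally, the average difference from week 0 to week 1 (absolute difference) for the study sample will be estimated and summarized".
- Its general rule on change outcomes uses absolute differences "where baseline distribution of proportion is close to 0 or 1, and relative (and absolute secondarily), changes otherwise".
- The one between-group tool is the general text on associations, "testing for differences in the distribution of the continuous covariate by varying levels of the categorical covariate", by an exact Kruskal-Wallis test. The baseline proportion appears nowhere as a covariate or stratifier.
- The expected values are given. For untreated liver, Section 8.8 reports "21-45% of all hepatocytes were infected". For Day 7, Section 4.2 reports from an earlier study: "In both participants, the proportion of HCV-infected hepatocytes had decreased to only 1" per cent.

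**The concern.** When the second value is near a floor, the absolute fall is the baseline minus almost a constant. It then carries little information on how fast infected cells cleared. The two hypotheses ask which group clears more; a contrast in absolute change may mostly answer which group started higher.

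The consequence differs by contrast. A and B are randomised, so a baseline difference is chance and costs precision. B and C differ by HIV status, so a baseline difference could be systematic and would pass almost one for one into the contrast. Section 4.1 says that HIV worsens HCV infection, among other ways, "by increasing the HCV RNA level". That makes a difference in infected-cell proportion conceivable but does not establish one.

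**Working it through.** **The plan's own figure.** Section 10.0 assumes a proportion of 0.5 and 400 cells. SE per person = √(2 × 0.5 × 0.5 / 400) = 0.0354. SE of a mean of five = 0.0354/√5 = 0.0158. Half-width = 1.96 × 0.0158 = 0.031, as stated (the printed 0.015 is truncated). This covers cell sampling within one group. It says nothing about a contrast between groups whose members start at different levels.

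**Floor arithmetic.** From 21% to 1% is 20 points, a relative fall of 20/21 = 95%. From 45% to 1% is 44 points, a relative fall of 44/45 = 98%. The absolute change more than doubles; the relative change hardly moves.

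**Slower clearance, larger fall.** With first-order clearance, a baseline of 30% at 0.50/day falls 30 × (1 − e^−3.5) = 29.1 points by Day 7. A baseline of 40% at the slower 0.45/day falls 40 × (1 − e^−3.15) = 38.3 points.

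**Variance of a 5 v 5 contrast, everyone ending at 1%.** Assume baseline uniform on 21-45% and 400 independent cells per biopsy.
- Variance of true baseline: (0.24)²/12 = 0.0048.
- Baseline cell sampling: (0.33 − 0.33² − 0.0048)/400 = 0.00054.
- Second-biopsy sampling: 0.01 × 0.99/400 = 0.000025.
- Variance of the change: 0.00537. Contrast SD = √(0.00537 × 2/5) = 0.046.
- Share not explained by measured baseline: 0.000025/0.00537 = 0.5%, so baseline explains 99.5%.
- SD of a contrast in the second-biopsy proportion: √(0.000025 × 2/5) = 0.003, about 15 times smaller.
- If B ends at 1% and A at 0%, the effect is 0.01, and 0.01/0.046 = 0.22 SD. The absolute-change contrast has the wrong sign in about 41% of trials.

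**Dependence on the second value** (simulation, baseline 21-45%):

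| Second-biopsy proportion | Contrast variance due to baseline |
|---|---|
| 1% in all | 99.5% |
| 3 at 1% on Day 7, 2 on Day 4, log-linear fall | 99% |
| same, linear fall | 91% |
| spread over 0-5% | 95% |
| spread over 0-10% | 85% |
| 0-60% of baseline remains | 44% |
| 20-80% of baseline remains | 29% |

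**Effect on conclusions.** Assumptions: three participants per group biopsied at Day 7 and two at Day 4, and a rate calibrated to fall from 33% to 1% in seven days (ln 33 / 7 = 0.50/day). The adjusted model regresses change on group, biopsy day and baseline.
- A clears 25% faster: true difference about 1.1 points, unadjusted SD 4.4 points, wrong sign 40%. Adjusted: SD 0.5 points, wrong sign 2%. Unadjusted relative change: 1%.
- A clears 50% faster: wrong sign 36-37% unadjusted, 0.1% adjusted.
- A clears 25% faster, with rates varying between people (SD 0.1/day): 39-40% unadjusted, 9-10% adjusted, about 8% on relative change.
- C starts 10 points higher (assumed) and clears 10% or 20% more slowly: unadjusted absolute change shows C falling more in about 96-97% of trials. Adjusted, the direction is right in 86% and 97%; on relative change, in 90% and 99.7%. With an assumed shift of 5 points, the unadjusted result still misleads in 75-81%.

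**The case against.** **No primary group comparison is written.** The sentence on the average difference is pooled over the study sample, the objective is estimation, and Section 10.0 calls the study exploratory. This stands: a reader might infer that Section 11 tests group differences in the primary change, and it does not say so. What remains is that the comparisons are stated aims with no suited analysis, and that the only tool at hand ignores baseline.

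**The plan already has a partial remedy.** Its general rule puts relative change first at baselines of 21-45%, and relative change does as well as the adjusted model above. Individual values and time-point summaries are also reported. This stands in part. The rule conflicts with the absolute difference named for the primary outcome, so it cannot be relied on, and the time-point summaries are across subjects, not by group. Relative change is also fragile at low baselines: over 1.7-21.6%, the range Section 4.1 cites from another method, the SD of its contrast is 0.11 against 0.011 over 21-45%, with all ending at 1%.

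**The near-total dependence on baseline is conditional.** The 1% comes from two coinfected participants on a different regimen at Day 7, and six of the 15 here are biopsied at Day 4. This stands, and the lower rows of the table show it.

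**The gain from adjustment is optimistic.** Section 8.8 reports that infected cells cluster. With an assumed within-grid correlation of 0.1, the adjusted wrong-sign rate at 25% faster clearance rises from 2% to about 23%. This stands; unadjusted absolute change is still worse there, at about 44%.

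**Conclusion.** The point holds as a gap and an internal conflict in Section 11. The stated A-B and B-C aims have no analysis that accounts for baseline, and the scale of the primary change is given two ways. If infection falls to near 1%, baseline accounts for roughly 91-99% of the variance of an absolute-change contrast; if a substantial and variable fraction remains, 29-44%. These figures assume a uniform baseline of 21-45% and 400 independent cells.

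Two stronger readings are not supported. The A-B contrast is not biased: allocation is randomised, and imbalance there is noise, though in the 25%-faster scenario about four times the effect sought (4.4 v 1.1 points). Nor do the documents show that B-C will be reversed. Section 4.1 speaks of HCV RNA level, no infected-cell proportion by HIV status is given, and the 5- and 10-point shifts are assumptions that illustrate sensitivity.

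**What to change.** In Section 11:
1. Keep the raw individual differences as description.
2. State which scale is primary for the infected-cell proportion, so that the general rule and the primary-outcome paragraph agree.
3. Base the A-B and B-C contrasts on one pre-named measure: either the second-biopsy proportion (equivalently the change) adjusted for baseline proportion and biopsy day, or relative change compared within biopsy day.
4. For A-B only, take the p-value by permuting group labels within biopsy day (20 × 6 = 120 arrangements).
5. Report B-C as a descriptive adjusted association, with an estimate and interval and no claim of an exact test. Labels are not exchangeable there: with C assumed 10 points higher at baseline and no true effect, a nominal 5% permutation test rejects about 14% of the time.

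The cost is wording and one small model. Baseline is already measured in everyone. With 10 participants per contrast, residual degrees of freedom fall from 8 to 6 if both covariates enter, or to 7 with one. The contrasts remain exploratory, and the precision gained will be smaller if infected cells cluster. Where a variable 0-60% or 20-80% of infection remained, adjustment still did not cost precision (SD 4.2 v 5.1 and 4.4 v 4.8 points).

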Visits during Step 2 must be scheduled on the exact day planned with no visit window. Entry/day 0 and day 7 are to be scheduled 7 days apart. If a participant misses a visit on days 1-6, they will continue on study. Missing a visit does not extend the total duration.

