These assumptions give an estimated within-subject standard error of 0.035 for the primary outcome and can be used to formulate a confidence interval on the difference in proportions of HCV-infected hepatocytes between week 1 and baseline on a single individual. For other less conservative assumptions (larger number of hepatocytes sampled, or estimated proportion of HCV-infected hepatocytes being either larger or smaller than 0.5 at either week 1 or week 0), the within subject standard error for the difference in proportions outcome would be smaller than 0.035, and so this represents the maximum standard error for the given assay parameters that specify that at least 400 hepatocytes will be measured in each subject at each time point.

For combining the estimated differences across subjects in order to obtain a study sample estimate for the difference in proportion of HCV positive hepatocytes between week 1 and baseline, the average difference across the 5 subjects within each group will be calculated. Assuming independence across individuals, and using the above maximum within subject standard error for each of the 5 subjects gives a standard error for the average as  $0.035/\sqrt{5}$ , which is 0.015. This was obtained using conservative assumptions for the purpose of sample size considerations in this exploratory study. Therefore, the estimated maximum half-width of a two-sided 95% confidence interval on the study sample average difference in proportion is approximately  $1.96 \times 0.015 = 0.031$ .

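### The primary week-1 average includes Day 4 biopsies in 6 of 15 subjects, and the A–B and B–C comparisons are given no confidence interval

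*Combined protocol and SAP*

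**What the plan says.** The primary objective (3.1, under Section 2.0) is the one-week change in the proportion of infected hepatocytes. Hypotheses 2.1 and 2.2 (under Section 1.0) are comparisons between groups at one week: three drugs against two (A v B), and HCV alone against HIV/HCV (B v C). Section 10.0 states that the groups permit both comparisons.

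Section 7.1 assigns the first nine subjects to Cohort 1 (3 per arm) and the next six to Cohort 2 (2 per arm). Section 7.2 places the second biopsy at Day 7 in Cohort 1 and Day 4 in Cohort 2. Section 4.2 gives the reason for Day 4: "this earlier time point will allow better understanding of this rapid and profound reduction in HCV burden".

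For the primary outcome, Section 11.0 lists 15 per-subject differences with their intervals and a summary of proportions at each time point. It adds that "the average difference from week 0 to week 1 (absolute difference) for the study sample will be estimated and summarized". Section 10.0 says "the average difference across the 5 subjects within each group will be calculated", and reports 0.031 as the maximum "half-width of a two-sided 95% confidence interval on the study sample average difference in proportion".

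On comparisons, Section 11.0 offers exact intervals on change outcomes, summaries by category, and "testing for differences in the distribution of the continuous covariate by varying levels of the categorical covariate using the exact version of Kruskal-Wallis test". On scale, where baseline is not near 0 or 1 it calls for "relative (and absolute secondarily), changes otherwise". Section 7.2 adds: "If a participant misses a visit on days 1-6, they will continue on study".

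**The concern.** Two things are missing. First, the analysis text does not recognise that the second biopsy falls on two different days. Day 4 was added because it should show an earlier stage of the decline, so by the protocol's own reasoning it measures a different quantity from the one-week change. Averaging the two under a week-1 label misstates the primary estimate.

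Second, the study is justified by precision and not by power, so intervals are its main product. The two comparisons that it was built for have no defined estimator and no interval. With 5 subjects per arm, leaving the contrast, the scale and the handling of biopsy day open until the data are seen allows much discretion.

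**Working it through.** **The plan's own figure.** Inputs from Section 10.0: 50% infected, 400 cells per biopsy, variance of the difference taken as twice the single-time variance.
- Within-subject SE = √(2 × 0.25/400) = 0.0354 (plan: 0.035).
- SE for a mean of 5 = 0.0354/√5 = 0.0158. The plan prints 0.015, a truncation.
- Half-width = 1.96 × 0.0158 = 0.031, as printed. The printed product 1.96 × 0.015 would give 0.029.
- The 0.031 therefore belongs to one group of 5. For 15 subjects the same formula gives 1.96 × 0.0354/√15 = 0.018.

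**Size of the mislabelling.** The Day 4 share is 6/15 = 2/5 = 0.40, so the result is the same for an average of 15 or of 5. Inputs: baseline 21–45% (Section 4.1) and 1% at Day 7 (Section 4.2, two subjects on another regimen). Exponential clearance is an assumption.
- Rate k = ln(p0/0.01)/7 = 0.435 per day (p0 = 0.21) to 0.544 per day (p0 = 0.45).
- Day 4 proportion = p0 × exp(−4k) = 3.7% to 5.1%.
- Shortfall = 0.40 × (Day 4 proportion − 1%) = 1.1 to 1.6 points.
- If 75% of the Day 7 log decline is reached by Day 4, the shortfall is 0.5–0.6 points; if 90%, 0.1–0.2 points.
- A straight-line fall is the slow extreme: 0.40 × (3/7) × (p0 − 0.01) = 3.4 to 7.5 points. Section 4.2 describes the fall as rapid, which points away from it.

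For comparison, the simulated half-width for a mean of 15 is about 4 points (0.039–0.045).

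**Precision of a 5 v 5 contrast.** Under the plan's maximum SE, the cell-sampling part is 1.96 × 0.0354 × √(2/5) = 0.044. This is a ceiling. At baseline 21–45% and the Day 7 and Day 4 proportions above, it is 0.026–0.034. With 1,000 cells at 50% it is 0.028. Between-subject variation comes on top and is not given in the documents. Assuming an SD of change of 0.05, 0.10 or 0.15, the half-width t(8 df) × √(SD² + 0.0354²) × √(2/5) is 0.089, 0.155 or 0.225. A three-group model with a cohort term (11 df) gives 0.085, 0.148 or 0.215.

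**Does ignoring biopsy day harm the contrasts?** This was simulated for A–B with assumed clearance of 0.6 v 0.4 per day, between-subject SD of the rate 0.05 to 0.20, baseline uniform on 21–45%, and 400 cells. Median half-widths, unadjusted v cohort-adjusted, at the lowest and highest SD:

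| Scale and shape | SD 0.05 | SD 0.20 |
|---|---|---|
| Absolute change, exponential | 0.102 v 0.101 | 0.120 v 0.119 |
| Percent reduction, exponential | 0.101 v 0.054 | 0.201 v 0.181 |
| Percent reduction, 75% by Day 4 | 0.054 v 0.042 | 0.168 v 0.166 |
| Percent reduction, 90% by Day 4 | 0.037 v 0.036 | 0.153 v 0.155 |

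**Loss of balance.** One missed Day 4 biopsy in one arm changes that arm's Day 4 share from 2/5 to 1/4. With Day 4 minus Day 7 gaps of 0.027–0.041, an unadjusted contrast moves by (0.40 − 0.25) × gap = 0.4–0.6 points.

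**The case against.** The strongest reply is that this is a declared exploratory study whose primary objective is to estimate change, not to contrast arms. All 15 changes will be listed with intervals. Reporting proportions at each time point can be read as separating Day 4 from Day 7. Section 11.0 also gives summaries by category and an exact group test. All of this stands, and it limits the harm. It does not supply the missing pieces: the time-point summary covers proportions and not the average change, and a Kruskal-Wallis test gives neither an estimated difference nor an interval.

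A reader might go further than the documents allow in three ways.
- That biopsy day biases A–B or B–C. It does not with complete data, because every arm has the same 3:2 split. Section 7.2 keeps a participant who misses a Day 1–6 visit on study, so balance is not guaranteed, but the shift computed above is small.
- That the plan certainly pools both regimens into one average of 15. Section 10.0 builds its study-sample estimate from averages within each group, so Section 11.0 can be read either way.
- That 0.044 is the least half-width a contrast can have. It comes from the plan's maximum SE and is the most that cell sampling can contribute.

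**Conclusion.** The point holds and should be fixed; its size is modest. That 40% of second biopsies in the primary average are at Day 4 follows from the cohort allocation and the count of 15 differences, and does not depend on how the study sample is read. The absence of an interval for A–B and B–C, and of any reference to cohort, is plain from Sections 10.0 and 11.0.

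The shortfall of 1.1–1.6 points rests on assumed exponential clearance and on a Day 7 value from two subjects on another regimen. It is below the simulated half-width of about 4 points and shrinks if most of the decline is over by Day 4. Adjusting for cohort gains almost nothing on absolute change. On relative change it can narrow the interval, depending on the shape of clearance. The case therefore rests on a mislabelled estimate and unspecified contrasts, not on bias or lost power.

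**What to change.** **Section 11.0**
1. Report change by group, separately for Day 4 and Day 7, and reserve the week-1 label for Day 7.
2. Name A–B as randomised and B–C as non-randomised. Give each a difference with a 95% interval from a model with arm and cohort. Make absolute change the main scale and define relative change in advance, including a rule for zero infected cells if a log or fold version is used.
3. If a test is reported, permute within cohort.
4. Show each contrast by biopsy day as a point estimate with individual data. Exact intervals reach at most 90% (3 v 3) and 67% (2 v 2).
5. Do not present the interval from the 13 within-cohort pairwise differences (2nd smallest to 2nd largest) as an exact 95% interval for percent change. It assumes a common shift, and on that scale the arm effect differs by day. In simulation under the exponential scenario it covered the 3:2-weighted mean difference 94%, 92% and 86% of the time at SD 0.05, 0.10 and 0.20.

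**Section 10.0**
Delete the description as single-arm and state that 0.031 is for one group of 5. Add that the cell-sampling part of a 5 v 5 contrast half-width is at most 0.044 under the plan's maximum SE, with between-subject variation extra.

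**Cost**
Wording and one standard analysis; no new subjects, visits or data. If biopsy day has no effect, model-based A–B intervals are about 1–3% wider. The permutation distribution is coarser: 120 v 252 allocations, so the smallest two-sided p is 2/120 = 0.017 instead of 2/252 = 0.008.
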